4. POMALIDOMIDE EDUCATION AND COUNSELING GUIDANCE DOCUMENT FOR MALE SUBJECTS

To be completed prior to each dispensing of pomalidomide.

Protocol Number: _____

Subject Name (Print): _____ DOB: _____ / _____ / _____ (dd/mmm/yyyy)

1. I have verified and counseled the subject regarding the following:

- Potential risk of fetal exposure to pomalidomide: A teratogenic potential of pomalidomide in humans cannot be ruled out. If pomalidomide is taken during pregnancy, it may cause birth defects or death to any unborn baby.
- The subject confirmed that he has practiced complete abstinence (True abstinence is acceptable when this is in line with the preferred and usual lifestyle of the subject. Periodic abstinence [eg calendar, ovulation, symptothermal or post-ovulation methods] and withdrawal are not acceptable methods of contraception.) or used a condom when engaging in sexual contact (including those who have had a vasectomy) with a pregnant female or FCBP, while taking pomalidomide, during dose interruptions and for at least 28 days after the last dose of pomalidomide.
- The subject confirmed that he has not impregnated his female partner while in the study.
- The subject confirmed that he will notify his study doctor if his female partner becomes pregnant and the female partner of a male subject taking pomalidomide confirmed that she will call her healthcare provider immediately if she becomes pregnant.
- The subject has not and will never share pomalidomide with anyone else.
- The subject confirmed that he has not donated and will not donate semen or sperm while taking pomalidomide or during dose interruptions and that he will not donate semen or sperm for at least 28 days after the last dose of pomalidomide.
- The subject has not and will not donate blood while taking pomalidomide, during dose interruptions and for at least 28 days after the last dose of pomalidomide.
- The subject has not and will not break, chew, or open pomalidomide capsules at any point.
- The subject confirmed that he will return unused pomalidomide capsules to the study doctor.

2. I have provided the Pomalidomide Information Sheet to the subject.

Global PPP Pomalidomide Adult
Celgene Corporation

Protocol [#]
Version 4.0 – Approved: 30 October 2014
Effective Date: 19 December 2014

Do Not Dispense Pomalidomide if:

- The subject stated that he has or does not want to adhere to pregnancy precautions outlined within this PPP.

Counselor Name (Print): _____

Counselor Signature: _____ Date: ____ / ____ / ____ (dd/mmm/yyyy)

Maintain a copy of the Education and Counseling Guidance Document in the subject's records.

Confidential and Proprietary

12

10.16 APPENDIX 16: PATIENT REPORTED OUTCOMES

10.16.1 European Organization for Research and Treatment of Cancer core quality of life questionnaire (EORTC QLQ-C30)

ENGLISH

EORTC QLQ-C30 (version 3)

We are interested in some things about you and your health. Please answer all of the questions yourself by circling the number that best applies to you. There are no "right" or "wrong" answers. The information that you provide will remain strictly confidential.

Please fill in your initials:

Your birthdate (Day, Month, Year):

--	--	--	--	--

Today's date (Day, Month, Year):

31

--	--	--	--	--

1. Do you have any trouble doing strenuous activities, like carrying a heavy shopping bag or a suitcase?
2. Do you have any trouble taking a long walk?
3. Do you have any trouble taking a short walk outside of the house?
4. Do you need to stay in bed or a chair during the day?
5. Do you need help with eating, dressing, washing yourself or using the toilet?

Not at All	A Little	Quite a Bit	Very Much
1	2	3	4
1	2	3	4
1	2	3	4
1	2	3	4
1	2	3	4

During the past week:

6. Were you limited in doing either your work or other daily activities?
7. Were you limited in pursuing your hobbies or other leisure time activities?
8. Were you short of breath?
9. Have you had pain?
10. Did you need to rest?
11. Have you had trouble sleeping?
12. Have you felt weak?
13. Have you lacked appetite?
14. Have you felt nauseated?
15. Have you vomited?
16. Have you been constipated?

Not at All	A Little	Quite a Bit	Very Much
1	2	3	4
1	2	3	4
1	2	3	4
1	2	3	4
1	2	3	4
1	2	3	4
1	2	3	4
1	2	3	4
1	2	3	4
1	2	3	4
1	2	3	4
1	2	3	4

Please go on to the next page

ENGLISH

During the past week:

During the past week:	Not at All	A Little	Quite a Bit	Very Much
17. Have you had diarrhea?	1	2	3	4
18. Were you tired?	1	2	3	4
19. Did pain interfere with your daily activities?	1	2	3	4
20. Have you had difficulty in concentrating on things, like reading a newspaper or watching television?	1	2	3	4
21. Did you feel tense?	1	2	3	4
22. Did you worry?	1	2	3	4
23. Did you feel irritable?	1	2	3	4
24. Did you feel depressed?	1	2	3	4
25. Have you had difficulty remembering things?	1	2	3	4
26. Has your physical condition or medical treatment interfered with your family life?	1	2	3	4
27. Has your physical condition or medical treatment interfered with your social activities?	1	2	3	4
28. Has your physical condition or medical treatment caused you financial difficulties?	1	2	3	4

For the following questions please circle the number between 1 and 7 that best applies to you

29. How would you rate your overall health during the past week?

A horizontal scale with seven points labeled 1 through 7. The first point is labeled 'Very poor' and the last point is labeled 'Excellent'. A large, semi-transparent letter 'S' is centered over the scale.

30. How would you rate your overall quality of life during the past week?

1	2	3	4	5	6	7
Very poor						Excellent

10.16.2 European Organization for Research and Treatment of Cancer quality of life myeloma module (EORTC QLQ-MY20)

ENGLISH

EORTC QLQ – MY20

Patients sometimes report that they have the following symptoms or problems. Please indicate the extent to which you have experienced these symptoms or problems during the past week. Please answer by circling the number that best applies to you.

During the past week:	Not at All	A Little	Quite a Bit	Very Much
31. Have you had bone aches or pain?	1	2	3	4
32. Have you had pain in your back?	1	2	3	4
33. Have you had pain in your hip?	1	2	3	4
34. Have you had pain in your arm or shoulder?	1	2	3	4
35. Have you had pain in your chest?	1	2	3	4
36. If you had pain did it increase with activity?	1	2	3	4
37. Did you feel drowsy?	1	2	3	4
38. Did you feel thirsty?	1	2	3	4
39. Have you felt ill?	1	2	3	4
40. Have you had a dry mouth?	1	2	3	4
41. Have you lost any hair?	1	2	3	4
42. Answer this question only if you lost any hair: Were you upset by the loss of your hair?	1	2	3	4
43. Did you have tingling hands or feet?	1	2	3	4
44. Did you feel restless or agitated?	1	2	3	4
45. Have you had acid indigestion or heartburn?	1	2	3	4
46. Have you had burning or sore eyes?	1	2	3	4

Please turn to next page

ENGLISH

During the past week:	Not at All	A Little	Quite a Bit	Very Much
47. Have you felt physically less attractive as a result of your disease or treatment?	1	2	3	4
48. Have you been thinking about your illness?	1	2	3	4
49. Have you been worried about dying?	1	2	3	4
50. Have you worried about your health in the future?	1	2	3	4

SPECIMEN

© Copyright 1999 EORTC Study Group on Quality of Life. All rights reserved.

10.16.3 European Quality of Life Group measure with 5 dimensions and 5 levels per dimension (EQ-5D-5L)

Health Questionnaire

English version for the UK

© 2009 EuroQol Research Foundation. EQ-5D™ is a trade mark of the EuroQol Research Foundation. UK (English) v1.2

Under each heading, please tick the ONE box that best describes your health TODAY.

MOBILITY

I have no problems in walking about
I have slight problems in walking about
I have moderate problems in walking about
I have severe problems in walking about
I am unable to walk about

SELF-CARE

I have no problems washing or dressing myself
I have slight problems washing or dressing myself
I have moderate problems washing or dressing myself
I have severe problems washing or dressing myself
I am unable to wash or dress myself

USUAL ACTIVITIES (e.g. work, study, housework, family or leisure activities)

I have no problems doing my usual activities
I have slight problems doing my usual activities
I have moderate problems doing my usual activities
I have severe problems doing my usual activities
I am unable to do my usual activities

PAIN / DISCOMFORT

[figure not shown]
I have no pain or discomfort
I have slight pain or discomfort
I have moderate pain or discomfort
I have severe pain or discomfort
I have extreme pain or discomfort

ANXIETY / DEPRESSION

I am not anxious or depressed
I am slightly anxious or depressed
I am moderately anxious or depressed
I am severely anxious or depressed
I am extremely anxious or depressed

- We would like to know how good or bad your health is TODAY.
- This scale is numbered from 0 to 100.
- 100 means the best health you can imagine.
0 means the worst health you can imagine.
- Please mark an X on the scale to indicate how your health is TODAY.
- Now, write the number you marked on the scale in the box below.

YOUR HEALTH TODAY =

10.16.4 Health Resource Utilization and Productivity Questionnaire (HRUPQ)

Health Resource Utilization & Productivity Questionnaire

Please answer the following questions and statements. Answer as honestly as you can without assistance from anyone else. Remember, there are no right or wrong answers; the answers should be based on your own personal experience.

Section 1. Baseline Health Care Utilization

[To be completed at Cycle 1 Day 1 before treatment]

Instructions: The following questions ask you about your health care use in the past 6 months. If you do not know the exact answer to a question, please give your best estimate. Answer as honestly as you can without assistance from anyone else.

I. During the past 6 months, how many times have you...

1. received care in a clinic or hospital emergency room to receive urgent care for any health issue (including Multiple Myeloma)? (Include emergency room visits that resulted in a hospital admission. (Enter '0' for None)	_____ times
2. received care at a clinic or hospital emergency room due to Multiple Myeloma? (Enter '0' for None)	_____ times
3. received at-home care from a nurse or other health professional for any health issue (including Multiple Myeloma)? (Enter '0' for None)	_____ times
4. # times you have received at-home care from a nurse or other health professional due to Multiple Myeloma? (Enter '0' for None)	_____ times

II. During the past 6 months, how many nights have you

5. stayed in hospital for any health issue (including Multiple Myeloma) ? (Enter '0' for None)	_____ nights
6. stayed in hospital (from Q5) due to Multiple Myeloma? (Enter '0' for None)	_____ nights
7. # stayed in the intensive care unit (ICU)? (Enter '0' for None)	_____ nights
8. stayed in the ICU (from Q7) due to multiple myeloma? (Enter '0' for None)	_____ nights

III. During the past 6 months, how many times have you seen or talked to following health care professionals?

9. A general doctor or primary care clinician who treats a variety of illnesses, such as a doctor or nurse practitioner in general practice, family medicine, or internal medicine for any health issue (including Multiple Myeloma) (other than an urgent care center clinician. Enter '0' for None)	_____ times
10. A general doctor or primary care clinician who treats a variety of illnesses, such as a doctor or nurse practitioner in general practice, family medicine, or internal medicine for a health issue related to multiple myeloma (other than an urgent care center clinician. Enter '0' for None)	_____ times
11. A physical or occupational therapist for any health issue (including Multiple Myeloma) (Enter '0' for None)	_____ times
12. A physical or occupational therapist for a health issue related to multiple myeloma (Enter '0' for None)	_____ times
13. A mental health professional, such as a psychiatrist, psychologist, psychiatric nurse, or clinical social worker for any health issue (including Multiple Myeloma) (Enter '0' for None)	_____ times
14. A mental health professional, such as a psychiatrist, psychologist, psychiatric nurse, or clinical social worker for a health issue related to multiple myeloma (Enter '0' for None)	_____ times
15. A medical doctor or clinician who specializes in a particular medical disease or issue for any health issue (including Multiple Myeloma) (other than a mental health professional, physical therapist, occupational therapist, or urgent care center clinician) (Enter '0' for None)	_____ times
16. A medical doctor or specialist clinician for a health issue related to multiple myeloma (other than a mental health professional, physical therapist, occupational therapist, or urgent care center clinician) (Enter '0' for None)	_____ times

Section 2. During Isatuximab administration visit and End of Trial (EoT) visits: Health Care Resource Utilization

Regarding the last Isatuximab administration:

17. How long was your hospital visit (from arrival to departure)?	...minutes
18. How long were you monitored for, after the administration of the treatment?	...minutes

19. Since the last Isatuximab administration, have you had a visit with a healthcare professional not required by the clinical trial?

August 26, 2022

2

Yes
 No

[SKIP LOGIC: If Item 19 = "no", skip to Section 3; else Item 20]

If yes, how many times have you:

20. received care in a clinic or hospital emergency room to receive urgent care for any health issue (including Multiple Myeloma)? (Include emergency room visits that resulted in a hospital admission. Do not include visits to urgent care centers. Enter '0' for None)	_____ times
21. received care at a clinic or hospital emergency room to receive urgent care due to Multiple Myeloma? (Enter '0' for None)	_____ times
22. received at-home care from a nurse or other health professional for any health issue (including Multiple Myeloma)? (Enter '0' for None)	_____ times
23. received at-home care from a nurse or other health professional due to Multiple Myeloma? (Enter '0' for None)	_____ times

24. Did any of these visits take place within 24 to 48 hours after last Isatuximab administration?

Yes
 No

[SKIP LOGIC: If Items 20 and 21 = 0, skip to Item 29; else Item 25]

If you have been hospitalized overnight, how many nights have you

25. stayed in hospital for any health issue (including Multiple Myeloma)? (Enter '0' for None)	_____ nights
26. stayed in hospital (from Q24) due to Multiple Myeloma? (Enter '0' for None)	_____ nights
27. stayed in the intensive care unit (ICU)? (Enter '0' for None)	_____ nights
28. stayed in the ICU (from Q26) due to multiple myeloma? (Enter '0' for None)	_____ nights

Excluding visits related to your Isatuximab treatment and the clinical trial, since the last Isatuximab administration, how many times have you seen:

August 26, 2022

29. A general doctor or primary care clinician who treats a variety of illnesses, such as a doctor or nurse practitioner in general practice, family medicine, or internal medicine (other than an urgent care center clinician. Enter '0' for None)	_____ times
30. A physical or occupational therapist (Enter '0' for None)	_____ times
31. A mental health professional, such as a psychiatrist, psychologist, psychiatric nurse, or clinical social worker (Enter '0' for None)	_____ times
32. A medical doctor or specialist clinician or issue (other than a mental health professional, physical therapist, occupational therapist, or urgent care center clinician) (Enter '0' for None)	_____ times

33. Since the last Isatuximab administration, have you had any health tests or procedures not mandated by the clinical trial (blood test, imagery, diagnostic tests etc.)?

Yes

No

[SKIP LOGIC: If Item 33 = "No", skip to Section 3; else Item 34]

34. Add the number of times you have done different Blood, Imagery and Diagnostic tests or procedures not mandated by the clinical trial. If you do not know the exact answer to a question, please answer as best as you can. (Enter '0' for None since last Isatuximab administration)

How many blood tests have you had? (Enter '0' for None)	_____ number of times
How many imagery exams have you done? (e.g. MRI scan, CT scan, echography, PET scan, etc.) (Enter '0' for None)	_____ number of times
Other tests not already listed (e.g. Diagnostic tests): please specify which test(s) and the number of times it was done	

Section 3. During Isatuximab administration visit and End of Trial (EoT) visits: Employment

Instructions: The following questions ask about your employment. If you do not know the exact answer to a question, please answer as best as you can.

35. Are you retired?

Yes

No

August 26, 2022

[SKIP LOGIC: If Item 35= "yes", administer Item 36 and do not repeat in future visits; else skip to Item 37]

36. Did you retire earlier than you would have liked due to multiple myeloma?

Yes
 No

[SKIP LOGIC: If Item 35 = "yes", end and do not repeat Section 3 in future visits; else Item 37]

37. Since the last Isatuximab administration, did you work for pay at a job or business?

Yes
 No

[SKIP LOGIC: If Item 37 = "yes", administer Item 38-44; else skip to Item 45]

38. Since the last Isatuximab administration, how many hours per week did you work?

_____ number of hours per week

39. Since the last Isatuximab administration, did you reduce your weekly work hours because of any issue related to your multiple myeloma?

Yes
 No

40. Since the last Isatuximab administration, how many hours per week did you reduce your work because of any issue related to your multiple myeloma?

_____ number of hours per week reduced

41. Since the last Isatuximab administration, did you change the type of work you do because of any issue related to your multiple myeloma?

Yes
 No

[SKIP LOGIC: If Item 40 = "yes", administer Item 42; else skip to Item 43]

42. Since the last Isatuximab administration, was your income reduced as a result of changing the type of work you do?

Yes
 No

43. Since the last Isatuximab administration, how many days did you miss from work because of any issue related to your multiple myeloma? (Do not include any days you missed from work to participate in this study.)

August 26, 2022

_____ number of days missed from work

44. Since the last Isatuximab administration, how many days were you at work but less productive than you would like because of any issue related to your multiple myeloma?

_____ number of days

45. Since the last Isatuximab administration, did you not work for pay because of any issue related to your multiple myeloma?

[figure not shown]
- Yes
- No

46. What is the main reason you did not work last month? (Select one)

- Unemployed
- On temporary leave from work
- Permanently disabled
- Working at job or business but not for pay
- Work seasonally and off-season
- Other, please describe: _____

[figure not shown]
Please note if you are having any severe symptoms, side effects, health issues or other concerns, please be sure to discuss with your doctor or nurse. Answers to the questions/questionnaires completed on this device are not reviewed by your doctor or nurse (data to be analyzed by study statisticians at future prespecified time points).

[figure not shown]

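### Two on-treatment HRUPQ items cite the wrong parent question, and the urgent-care-center exclusion appears in only one of four emergency-visit items, so myeloma-related nights and visits may be misreported or inconsistent

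*Protocol*

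**What the plan says.** The HRUPQ is reproduced in Protocol Section 10.16.4. It has a baseline part, completed at Cycle 1 Day 1, and an on-treatment part on use since the last isatuximab administration.

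- **Baseline nights.** Item 5 asks for all hospital nights and Item 7 for all ICU nights. The myeloma items under them read "stayed in hospital (from Q5) due to Multiple Myeloma" (Item 6) and "stayed in the ICU (from Q7) due to multiple myeloma" (Item 8).
- **On-treatment nights.** Item 24 asks "Did any of these visits take place within 24 to 48 hours after last Isatuximab administration", answered Yes or No. Item 25 asks for nights "stayed in hospital for any health issue (including Multiple Myeloma") and Item 27 for nights "stayed in the intensive care unit (ICU"). The myeloma items read "stayed in hospital (from Q24) due to Multiple Myeloma" (Item 26) and "stayed in the ICU (from Q26) due to multiple myeloma" (Item 28).
- **Emergency visits.** On treatment, Item 20 (any cause) carries the instruction "Do not include visits to urgent care centers". Item 21 (myeloma) does not. At baseline, neither Item 1 (any cause) nor Item 2 (myeloma) carries it.

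Table 6 lists health resource utilization, measured by the HRUPQ, among the other secondary endpoints. Section 9.2.3.2 plans a descriptive summary only. Section 8.5 says the questionnaire was developed for this study, is completed by the participant and is collected electronically.

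**The concern.** The any-cause and myeloma-specific items are built as total and subset. That works only if each subset names the right total and both use the same definition of an event. On treatment, both conditions fail in places: two subset items name the wrong question, and one emergency total has an exclusion that its subset lacks.

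At stake is the quality of a listed secondary endpoint. Section 2.1 gives lower health resource use as one aim of subcutaneous administration, and Section 8.11 names the HRUPQ as the means of collecting hospitalizations and emergency visits. The form tells participants to answer without help, so staff are not expected to explain a misleading reference. A later analysis plan cannot recover what a participant meant by an answer to an inconsistent item.

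**Working it through.** The protocol gives no figure to reproduce, so the check compares the baseline and on-treatment items line by line.

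**Parent references**

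| Subset | Baseline item and cited parent | On-treatment item and cited parent | Total directly above it on treatment |
|---|---|---|---|
| Myeloma hospital nights | 6, cites Q5 (all hospital nights) | 26, cites Q24 (Yes/No, visit timing) | 25 |
| Myeloma ICU nights | 8, cites Q7 (all ICU nights) | 28, cites Q26 (myeloma hospital nights) | 27 |

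At baseline each subset cites the item one above: 6 − 5 = 1 and 8 − 7 = 1. On treatment the gap is two: 26 − 24 = 2 and 28 − 26 = 2. Both references are one number too low (25 − 24 = 1; 27 − 26 = 1), the pattern that a renumbering slip would leave.

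The two errors differ in effect. Item 24 contains no nights, so Item 26 is told to take a subset of something that is not a count. Item 28 is pointed at a real count, and myeloma ICU nights already lie within myeloma hospital nights, so its answer need not change.

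**Emergency-visit definition**

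| Item | Period | Cause | Urgent care centers excluded? |
|---|---|---|---|
| 1 | Past 6 months | Any | No |
| 2 | Past 6 months | Myeloma | No |
| 20 | Since last administration | Any | Yes |
| 21 | Since last administration | Myeloma | No |

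Take a participant whose only event is one myeloma-related visit to an urgent care center, and who regards it as emergency care.

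- On treatment, the instruction removes the visit from Item 20, and nothing removes it from Item 21. The record can read Item 20 = 0, Item 21 = 1: a subset larger than its total.
- At baseline, the same visit can be counted in both items: Item 1 = 1, Item 2 = 1.

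The recall periods differ by design and can be handled by using rates. The difference in definition cannot.

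Items 20 and 21 also control the skip before Item 25: if both are zero, the night questions are not shown. How a participant understands the exclusion therefore also bears on whether nights are asked about at all.

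**The case against.** The strongest reply is that these are proofreading slips with no demonstrated effect on the data.

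- Item 26 can be answered without its parenthesis, since its stem asks for hospital nights due to myeloma. This stands. A reader might infer that Item 26 collects only nights linked to visits in the 24-to-48-hour window, and might scale that window against the dosing interval to claim a large understatement. The documents do not support this. The item states no such restriction, Item 24 concerns visits and not nights, the window itself can be read in more than one way, and nothing is known about when admissions fall.
- Item 28's count can be right despite its reference. This also stands.
- Item 21 exceeds Item 20 only if a participant treats an urgent care center as a clinic or hospital emergency room and does not carry the preceding instruction forward. That makes the inconsistency possible, not certain.
- Item 1's parenthesis is unclosed in the text at hand, so a lost sentence cannot be ruled out there. This weakens the baseline comparison a little, but not the comparison of Item 20 with Item 21.
- The appendix is a specimen with programming notes, and the deployed ePRO may show different wording. This is a reason to check it, not to leave the printed form uncorrected.
- A reader might also infer that myeloma-related nights dominate cost. The protocol ranks no HRUPQ item by cost.

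What remains is that the printed items are wrong or inconsistent in a self-completed instrument for a listed endpoint.

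**Conclusion.** The wording defects are established: two wrong parent references (Items 26 and 28), and one exclusion given in Item 20 but not in Items 1, 2 and 21. The supportable consequence is that myeloma-related hospital nights and emergency visits **may** be misreported or internally inconsistent, and that baseline and on-treatment emergency counts are not on one definition. It is not shown that they are miscounted, and no size can be given.

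The importance is small. The endpoint is summarized descriptively, the same form serves both arms, and the HRUPQ is outside the testing hierarchy in Section 9.2.5, so no co-primary or key secondary conclusion can change. The conclusion assumes that the deployed questionnaire carries the printed wording, which the protocol alone cannot confirm.

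**What to change.** 1. Change the reference in Item 26 to Q25 and in Item 28 to Q27.
2. Use the same urgent-care-center instruction, whichever is intended, in Items 1, 2, 20 and 21.
3. Check whether the deployed ePRO carries the printed wording.
4. For data already collected, flag records in which Item 21 exceeds Item 20, report how many there are, and identify every response by questionnaire version. Nights in Item 25 with none in Item 26 should not be treated as an error, because a hospital stay unrelated to myeloma validly gives that pattern.

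The cost is an edit to a few item texts in the ePRO and its language versions, plus a short data check. The downside is two questionnaire versions in one dataset. Changing Items 1 and 2 helps only participants who have not yet reached Cycle 1 Day 1. The sponsor already revised this questionnaire in amended protocol 01 (Section 10.19.1), so such a change is feasible.

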8.11 HEALTH ECONOMICS OR MEDICAL RESOURCE UTILIZATION AND HEALTH ECONOMICS

Medical resource utilization will be collected through the specific HRUPQ questionnaire. Protocol-mandated procedures, tests, and encounters are excluded. The data collected will include number, nature (emergency or routine) and duration of hospitalizations, emergency room visits and outpatient medical encounters.

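### As printed, the HRUPQ skip rules make Item 42 unreachable and omit hospital nights on forms that report no emergency or urgent-care visit

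*Protocol*

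**What the plan says.** The HRUPQ is listed among the other secondary endpoints (Protocol Section 3, Table 6). Section 9.2.3.2 plans a descriptive summary only. Sections 8.5 and 8.11 both describe what it collects; Section 8.11 names the number, "nature (emergency or routine) and duration of hospitalizations", along with emergency-room visits and outpatient encounters. Section 8.5 also names employment history.

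The form itself is in Section 10.16.4.

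- **Employment part (Section 3 of the form).** Item 40 asks "how many hours per week did you reduce your work because of any issue related to your multiple myeloma", and its answer field is the "number of hours per week reduced". Item 41 is a yes/no question: "did you change the type of work you do because of any issue related to your multiple myeloma". The rule printed next makes a yes to Item 40 the condition to "administer Item 42; else skip to Item 43". Item 42 asks "was your income reduced as a result of changing the type of work you do".
- **On-study utilization part (Section 2 of the form).** Items 20 and 21 count urgent care at a clinic or emergency room, for any reason and for myeloma respectively. Items 25-28 ask for hospital and ICU nights. The rule between them is "If Items 20 and 21 = 0, skip to Item 29; else Item 25".
- **Baseline part (Section 1 of the form).** Items 5-8 ask for hospital and ICU nights with no such rule.

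**The concern.** A self-completed electronic form shows only what its routing allows. If the printed rules were programmed literally, two things would follow.

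The income question would never appear, so one productivity item would have no data. Inpatient stays would be asked about only when the same form also reports emergency or urgent care. A participant admitted electively or directly from clinic would enter 0 for Items 20 and 21 and go straight to outpatient contacts. That conflicts with the protocol's own statement that routine admissions and their length are collected. Section 2.1 also gives lower health resource use as one of the aims of the SC route, so the questionnaire should record inpatient use correctly.

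**Working it through.** There is no planned figure to reproduce. The check is to follow the printed routing.

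**1. Reaching Item 42.** Inputs are the printed answer options: Item 35 (retired) yes/no, Item 37 (worked for pay) yes/no, Item 40 a number of hours, Item 41 yes/no. For enumeration Item 40 was allowed to run from 0 to 80, which gives 81 values.

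- Number of paths: 2 × 2 × 81 × 2 = 648.
- Rule as printed (Item 40 must be yes): none of the 81 numeric values equals yes, so 0 of 648 paths reach Item 42.
- Rule moved to Item 41: the paths that reach Item 42 are not retired (1) × worked for pay (1) × any hours (81) × Item 41 yes (1) = 81 of 648.

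These are counts of possible routes, not proportions of participants. The wider instruction to administer Items 38-44 when Item 37 is yes does not help, because the narrower rule inside that block sends everyone on to Item 43.

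**2. Capturing hospital nights.** Take a 5-night stay reported on one on-study form with Item 19 = yes.

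| Item 20 | Item 21 | Items 25-28 shown? | Nights recorded |
|---|---|---|---|
| 0 | 0 | No, goes to Item 29 | not asked (0 of 5) |
| 1 | 0 | Yes | 5 |
| 1 | 1 | Yes | 5 |

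No later item on the form asks about nights, so the first row is not repaired further down. If Items 25-28 did not depend on Items 20-21, the first row would also record 5.

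**3. Size.** If a share p of on-study nights falls on forms where Items 20 and 21 are both 0, the form misses exactly that share. The documents give nothing from which to estimate p. It could lie anywhere from 0 to 1.

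**4. Back-references.** Item 26 points to Q24, which is a yes/no question on the timing of visits; the hospital-nights question is Item 25. Item 28 points to Q26; the ICU-nights question is Item 27. Both are one too low, as is Item 40 for Item 41. The pattern fits a renumbering that was not carried through, and it supports reading Item 41 as the intended gate.

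**The case against.** The best reply is that this is a slip in an appendix with little consequence, and much of that stands.

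- **The programmed form is not shown.** A yes condition on a numeric field would probably be noticed when the form was built. A reader might infer that trial data have been lost; the protocol shows only that the printed specification would lose them.
- **The two faults differ in kind.** Item 42 measures productivity. Its absence does not miscount health-resource use; only the Item 20-21 gate bears on that.
- **Not every non-emergency night is lost.** The gate works form by form. Anyone who reports an emergency or urgent-care visit in the interval, even an unrelated one, is asked about all nights.
- **Nights are partly recoverable.** Inpatient hospitalization is a seriousness criterion (Section 10.3.2), and events are collected from consent to 30 days after the last dose. However, elective admission for a pre-existing condition that has not worsened is excluded there, so the check is weakest for the planned stays that the gate drops. It cannot supply the income item.
- **Baseline comparison adds little.** Baseline recall covers 6 months and on-study recall covers the time since the previous isatuximab dose, so the counts were never directly comparable. The protocol states no change-from-baseline analysis of the HRUPQ.
- **The time-saving questions are intact.** Items 17 and 18, on length of visit and of monitoring, come before both gates.

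What the reply does not answer is that the Item 20-21 rule is not a numbering slip. It is workable, would pass a build check, and contradicts Sections 8.5 and 8.11.

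**Conclusion.** Both errors are present in the questionnaire as printed. Item 42 cannot be reached by any answer path. Items 25-28 are withheld on every on-study form where Items 20 and 21 are both 0, so a planned or direct admission with no emergency or urgent-care visit in that interval goes unrecorded, contrary to Sections 8.5 and 8.11.

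The size of the undercount of nights cannot be calculated from the documents. A reader might go further and infer a biased comparison of resource use between SC and IV. That is not supported: both arms use the same form and the same rule, and nothing in the protocol suggests that non-emergency admissions differ by route. The HRUPQ is summarised descriptively and lies outside the testing hierarchy, so the co-primary endpoints, the key secondary tests, the type I error rate and the sample size are unaffected. The conclusion rests on the printed appendix and assumes that the electronic build follows it.

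**What to change.** 1. Compare the programmed ePRO with Section 10.16.4 first. If the build already routes correctly, only the appendix needs correcting.
2. Make Item 42 depend on Item 41 = yes.
3. Ask Items 25-28 of everyone who answers yes to Item 19, or put a yes/no overnight-stay question in front of them, in place of the Item 20-21 condition.
4. Correct the back-references: Item 26 to Q25 and Item 28 to Q27.
5. If data were collected under the printed rules, use SAE hospitalization records as a partial check on nights. State in the report that non-emergency stays may be under-recorded and that Item 42 is missing by design of the form.

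The cost is a small reprogramming and a check of the translations. Forms completed before the change stay incomplete.
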